PLEASE FILE THIS LETTER AND ANY IRB CORRESPONDENCE IN YOUR REGULATORY FILE AND OTHER PERTINENT FILES. YOU ARE NOT REQUIRED TO SUBMIT THESE DOCUMENTS TO THE PROTOCOL REGISTRATION OFFICE UNLESS THE CHANGES RESULT IN A CHANGE TO THE INFORMED CONSENT FOR YOUR SITE.

Summary of Revisions

- The listing of study sites throughout the protocol is updated to not include Chililabombwe, Zambia.
- The protocol is clarified throughout to specify that chlamydia and gonorrhea testing will be performed
 by standard diagnostic methods in use at each study site, rather than by ligase chain reaction (LCR).
 Standard diagnostic methods to test for chlamydia and gonorrhea currently in use at each site are
 summarized in the following table:

Site	Chlamydia Test	Gonorrhea Test
Duban, South Africa	SDA	SDA
Hlabisa, South Africa	SDA	SDA
Lusaka, Zambia	ELISA	Culture
Moshi, Tanzania	ELISA	Culture

ELISA, Enzyme-linked Immunosorbent Assay; SDA, Strand Displacement Amplification

- The number of infections listed in Tables 1 and 2 of the protocol's statistical section is corrected.
- The Protocol Team Roster is updated.

Upon receipt of IRB/EC approval, the following protocol modifications, indicated by strikethrough and underscored text, will be implemented:

1. In the List of Abbreviations and Acronyms:

LCR ligase chain reaction

2. In the Protocol Team Roster:

[name], MS HPTN CORE Protocol Specialist (back-up)

[name]
HPTN CORE Protocol Specialist
Family Health International
[name]
[name]
[contact]
T: [contact] [name]

3. In the Schema:

Chililabombwe, Zambia

F: [contact]

4. In the Schema:

1200 participants total (240 participants per site).

5. In Section 2.2:

The is a prospective cohort study to be conducted at HPTN study sites located in Chililabombwe Zambia; Durban, South Africa; Hlabsia South Africa; Lusaka, Zambia; and Moshi, Tanzania.

- 6. In Section 4.2.2, add bullet:
 - Specimen collection for chlamydia and gonorrhea testing (by standard local method).
- 7. In Section 4.2.3, second bullet:
 - Urine ligase chain reaction (LCR) Chlamydia and gonorrhea testing by standard local method.
- 8. In Section 4.3.2, add bullet:
 - Specimen collection for chlamydia and gonorrhea testing (by standard local method).
- 9. In Section 4.3.3, second bullet:
 - Urine LCR Chlamydia and gonorrhea testing by standard local method if clinically indicated.

- 10. In Section 4.4.2, add bullet:

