3.2 Exclusion Criteria

Women who meet any of the following criteria will be excluded from this study:

- History of adverse reaction to latex.
- History of non-therapeutic injection drug use in the 12 months prior to screening.
- Had vaginal intercourse more than an average of two times per day in the two weeks prior to screening.
- At screening:
 - Plans to travel away from the study site for more than three consecutive months in the next 12 months.
 - Plans to relocate away from the study site in the next 12 months.
 - Plans to become pregnant in the next 12 months.
- At screening or enrollment:
 - Enrolled in any other study of a vaginally-applied product.
 - Pregnant.
- At enrollment, is within 42 days of last pregnancy outcome.
- At enrollment, has a clinically apparent pelvic exam finding involving deep epithelial disruption.

Note: Otherwise eligible participants with pelvic exam finding(s) involving deep epithelial disruption may be enrolled after the finding has resolved. If resolution is documented within 30 days after obtaining informed consent for screening, screening procedures need not be repeated.

• At enrollment, diagnosed with a current STD and/or other reproductive tract infection requiring treatment according to WHO guidelines.

Note: Participants will undergo laboratory testing for chlamydia, gonorrhea, and syphilis at their screening visits, and wet mount testing for BV, candidiasis, and trichomoniasis at their enrollment visits; all results will be available at the enrollment visits. Otherwise eligible participants diagnosed at their enrollment visits with infection(s) requiring treatment per WHO guidelines (other than asymptomatic candidiasis) will be offered treatment and may be enrolled after completing treatment and all symptoms have resolved. If treatment is completed and symptoms have resolved within 30 days after obtaining informed consent for screening, screening procedures need not be repeated.

• At enrollment, has any other condition that, in the opinion of the Investigator or designee, would preclude provision of informed consent, make participation in the study unsafe, complicate interpretation of study outcome data, or otherwise interfere with achieving the study objectives.

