3.3 Screening and Enrollment Process

Eligibility for the study will be assessed in a step-wise manner at the study Screening and Enrollment Visits. Although all required procedures may be completed in one Screening Visit and one Enrollment Visit, additional visits may be conducted if needed. For example, a participant may want more time to consider whether to participate in the study, may require treatment for an STD or other reproductive tract infection, or may not be able to undergo a pelvic exam due to menstruation. Regardless of the number of visits required, all screening and enrollment procedures must be completed within a 30-day period, beginning on the day the participant provides informed consent for screening. If a participant is not enrolled within 30 days after providing informed consent for screening, the screening process must be repeated.

After providing written informed consent for screening, potential study participants will be assigned an ID number and asked to provide demographic information, behavioral eligibility information, and locator information. They will undergo urine pregnancy testing and HIV and STD counseling and testing. Presumptively eligible participants will be scheduled to return for their Enrollment Visits approximately 7-14 days later, when all screening test results are expected to be available.

Note: For study screening purposes HIV infection status will be ascertained using two different rapid enzyme immunoassay tests; in the event that results from the two tests are discordant, a third test will be performed. Once a participant has enrolled in the study, follow-up HIV testing will be performed according to the algorithm in Appendix II.

At their Enrollment Visits, potential participants will be informed of their screening test results, in the context of post-test counseling, and again undergo testing for pregnancy. Those who test negative will undergo a pelvic exam with wet mount testing for BV, candidiasis, and trichomoniasis; colposcopy will be performed at selected sites. Pap smears will be performed at sites with the capacity and expertise to prepare and interpret the smears and provide appropriate follow-up care to participants with abnormal results.

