4.3.3 Laboratory Procedures

- Urine pregnancy test.
- Urine LCR for chlamydia and gonorrhea if clinically indicated.
- Dipstick urinalysis if clinically indicated; urine culture if dipstick is positive for leukocytes or nitrites.
- Gram stain assessment for BV according to the Nugent criteria at the HPTN Central Lab.
- Pap smear interpretation (at selected sites only).
- Syphilis serology if genital ulcer is observed.
- Plasma archive

Note: For participants who do not consent to long-term specimen storage and possible future research testing, archived plasma will be discarded after all protocol-required and quality assurance testing has been completed (see also Section 8.3).

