4.4 Follow-up Visits

Monthly follow-up visits are scheduled throughout the study follow-up period on the monthly anniversary dates of participants' study enrollment dates. For example, for a participant enrolled on September 15, follow-up visits will be targeted to take place on October 15, November 15, December 15, etc. For participants enrolled on the last day of a month with 31 days, follow-up visits will be targeted to take place on the last day of all subsequent months (e.g., February 28, April 30, June 30, September 30, November 30). Acknowledging that it will not always be possible to complete follow-up visits on the targeted dates, visits may be completed within a four-week window around the target date (i.e., \pm 2 weeks from the target date).

For participants who do not complete scheduled visits within the allowable window, the visit will be considered "missed" and relevant case report forms will be completed to document the missed visit. However, for participants who miss visits scheduled to take place in study months 3, 6, 9, and 12, the pelvic exam and HIV counseling and testing procedures specified to take place at these visits will be conducted at the participants' next visit. Accordingly, every effort should be made to conduct participants' next visit at the study site, rather than at a community-based location. If this is not possible, an interim on-site visit in which the pelvic exam and HIV counseling and testing procedures are performed should be conducted as soon as possible after the off-site visit.

Note: Participants who become pregnant or infected with HIV during follow-up may be maintained in this study until the initiation of HPTN 035. For participants who become pregnant, follow-up procedures may be modified according to guidelines specified in the study-specific procedures manual. For example, after 24 weeks of pregnancy, quarterly pelvic exams may be discontinued and blood collection may be limited to fingersticks for HIV serology only. For participants who become infected with HIV, HIV serology will be discontinued and counseling will be tailored to primary and secondary HIV/STD prevention for infected women.

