6.4.2 Secondary Analyses

Corresponding to the secondary study objectives, the following secondary analyses will be performed:

- The study accrual process will be described by tabulating the number and rate of potential participants screened for and enrolled in the study at each site, overall and by month during the accrual period. Each site's actual accrual rates will be compared to the target rates, and reasons for ineligibility for the study will be tabulated.
- The number of enrolled participants retained in the study will be tabulated for each site for the entire site-specific follow-up period as well as for each quarter in the follow-up period. Retention rates also will be calculated. The denominator for these calculations will be the total number of participants enrolled in the study at the site. The numerator will include all participants at the site who complete a scheduled visit during the interval and/or are known to have died during a previous interval. Retention rates for each site will be compared to the annual target of 95 percent.
- The demographic characteristics of persons screened for and/or enrolled in the study at each site will be described. At a minimum, the characteristics listed in Section 6.2 will be tabulated.
- The HIV risk behaviors of persons enrolled in the study at each site will be described. At a minimum, the frequency of each of the outcomes listed in Section 6.2 will be tabulated.
- The baseline prevalence for each of the genital signs and symptoms and infections listed in Section 6.2 will be computed for the enrolled study population at each site, as the total number of endpoints observed among enrollees divided by the number of participants enrolled. Appropriate 95% confidence intervals also will be computed. An incidence rate for each of the genital signs and symptoms and infections listed in Section 6.2 also will be computed for each study site, as the total number of endpoints observed divided by the total number of person-years of follow-up. Confidence intervals will be calculated based on Poisson distribution assumptions.

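### Chlamydia, gonorrhea and syphilis are last routinely tested at Screening, so infections from the Screening-to-Enrollment gap can be counted as incident with no matching person-time

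*Supplement*

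**What the plan says.** **Baseline testing.** The note in protocol Section 3.2 says: "Participants will undergo laboratory testing for chlamydia, gonorrhea, and syphilis at their screening visits". The same note places the wet mount for bacterial vaginosis, candidiasis and trichomoniasis at the Enrollment Visit.

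**Retesting at Enrollment.** For Section 4.3.3, the Letter of Amendment (item 9) gives "Chlamydia and gonorrhea testing by standard local method if clinically indicated". For syphilis, Section 4.3.3 has "Syphilis serology if genital ulcer is observed". Appendix I marks both as conditional. Item 8 of the Letter adds collection of a chlamydia and gonorrhea specimen at Enrollment without stating a condition, but the test itself stays conditional.

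**The gap.** Under Section 3.3, presumptively eligible women are "scheduled to return for their Enrollment Visits approximately 7-14 days later", and "all screening and enrollment procedures must be completed within a 30-day period" that begins with consent for screening.

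**Follow-up clock.** Section 4.4: "Monthly follow-up visits are scheduled throughout the study follow-up period on the monthly anniversary dates of participants' study enrollment dates". Section 4.3 labels Enrollment day 0. Routine retesting for the three infections is quarterly, so the first is at month 3 (Sections 2.2 and 4.4.3).

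**Analysis.** Section 6.2 treats findings at screening or enrollment as prevalent and findings during follow-up as incident. Section 6.4.2 then computes every incidence rate for each site "as the total number of endpoints observed divided by the total number of person-years of follow-up", with Poisson intervals.

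**HIV, by contrast.** Section 4.4.3 has the archived enrollment plasma tested when a woman is HIV-positive at month 3, and Section 8.3 has the Central Lab test the entry specimens of all seroconverters. No similar check is described for the three infections.

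**The concern.** A rate is coherent when the time in its denominator is the time over which its events could arise and be detected. For the wet-mount infections, the baseline test and the start of follow-up coincide. For chlamydia, gonorrhea and syphilis in a woman with no clinical indication at Enrollment, the month-3 test looks back to the Screening specimen, while counted time appears to begin only at Enrollment. An infection acquired in between and still present at month 3 adds to the numerator, and the days in which it was acquired do not add to the denominator.

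At stake are the site-specific incidence estimates for three secondary endpoints that describe the population intended for HPTN 035. The HIV seroincidence estimate is not affected.

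**Working it through.** **1. Reproduce the plan's denominators (Section 6.3).** Inputs are 240 women per site and 97.5% semi-annual retention.
- Six months: 240 × 0.5 × 0.975 = 117.0 woman-years (stated: 117).
- Twelve months: 240 × 1.0 × 0.975 = 234.0 woman-years (stated: 234).

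Exact Poisson limits with the amended counts also agree with Tables 1 and 2 to within 0.1 point. For example, 6 infections in 117 woman-years give 5.13% with limits 1.88-11.16% (printed 5.1%, 1.8-11.2%). The planning figures amount to 0.5 or 1.0 year per woman, less losses, with no pre-enrollment time. This supports, but does not state, a start at Enrollment.

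**2. Size of the gap component.** Uncovered time per site = 240 × gap / 365.25. Greatest relative excess = uncovered time / stated woman-years. This assumes constant risk, that every gap infection persists to month 3, and that none is caught at Enrollment.

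| Gap | Uncovered woman-years | Excess on 117 | Excess on 234 |
|---|---|---|---|
| 7 days | 4.6 | 3.9% | 2.0% |
| 14 days | 9.2 | 7.9% | 3.9% |
| 30 days (every woman) | 19.7 | 16.8% | 8.4% |

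The documents give no figure for persistence or for detection at Enrollment. If only half of gap infections stay undetected and persist, the excess falls to 2.0%, 3.9% and 8.4% on 117 woman-years, and to 1.0%, 2.0% and 4.2% on 234.

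**3. In cases.** The documents give no STD rate, so take 5.13% and 10.26% per year as assumptions (the rows for 6 and 12 infections in the amended Table 1). Extra cases = uncovered time × rate.
- At 5.13%: 0.24, 0.47 and 1.01 extra cases per site for gaps of 7, 14 and 30 days. The expected rate over 117 woman-years becomes at most 5.33%, 5.53% and 5.99%.
- At 10.26%: 0.47, 0.94 and 2.02 extra cases, and at most 10.66%, 11.07% and 11.99%.

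The printed intervals at these rates are 1.8-11.2% and 5.3-17.9%, so the shift is small beside sampling error.

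**4. The other end of follow-up.** The figures in step 2 suit follow-up that ends at a quarterly test, as it does at exactly 6 or 12 months. Section 2.2 also describes follow-up for at least six months from the end of accrual. Take its monthly targets (20, 30, 40, 50, 50, 50), enrollment at mid-month, closure six months after accrual and no losses.
- Months of follow-up by accrual month: 11.5, 10.5, 9.5, 8.5, 7.5, 6.5. Weighted mean = 8.54 months, about 260 days.
- Month of the last quarterly test: 9, 9, 9, 6, 6, 6. Mean = (90 × 9 + 150 × 6) / 240 = 7.125 months, about 217 days.
- Untested tail: 260 − 217 = 43 days on average.

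Routinely tested exposure over counted time = (217 + gap) / 260:
- 7 days: 224 / 260 = 0.86
- 14 days: 231 / 260 = 0.89
- 30 days: 247 / 260 = 0.95

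Even with every gap infection counted, the ratio is below 1. The net bias in this scenario is downward at each of these gaps, setting aside clinically indicated tests in the tail.

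**The case against.** **Inflated by construction?** A reader might infer that the three rates are bound to be too high. The documents do not support that. If the denominator is all follow-up time, it can include weeks after the last routine test, and step 4 shows this can more than cancel the gap. Net upward bias holds only where follow-up ends at a quarterly test. This objection stands.

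**No test after Screening?** A reader might also infer that the three infections go untested until month 3, or that at least 7 days always separate Screening from Enrollment. Neither is so. Conditional tests accompany the Enrollment pelvic exam and will catch some infections. The 7-14 days is an approximate planned interval, not a minimum, and 30 days is a ceiling. STD treatment is one stated reason for extra visits; for women treated before Enrollment, the relevant gap runs only from completion of treatment. The 30-day row is therefore an extreme.

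**Is the time origin left to an analysis plan?** No sentence says when person-time starts, and no separate analysis plan is shown. An infection-specific origin could properly be set there. This is why the start at Enrollment is called an inference. But Section 6.4.2 does state a formula and applies it to conditions whose baseline tests fall at different visits, and the protocol took care of the equivalent problem for HIV.

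**Are comparisons distorted?** Section 6.4.2 plans no comparison of STD incidence between sites or between infections. The sites also use different chlamydia and gonorrhea assays (Letter of Amendment) and may start before full proficiency in tests other than HIV (Section 8.1). Distorted comparison is not a harm to any planned analysis.

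**Does the remedy bring its own bias?** Partly. Gap infections caught at Enrollment are prevalent and leave the numerator, while women not caught contribute gap time. That conditions a little time on no detected event. Moving only the start would also leave the tail uncorrected and could make a downward bias worse, so both ends have to be tied to tests.

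**Conclusion.** The concern holds in limited form. The three infections are not routinely retested at Enrollment, and an undetected gap infection that persists to month 3 can be counted as incident without matching time at risk.

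Taken alone, this raises the rate by at most about 4-8% over six months or 2-4% over 12 months for the planned gap, and by about 17% or 8% if every woman had the 30-day maximum. These upper bounds rest on constant risk, full persistence, no detection at Enrollment and person-time that starts at Enrollment. At an assumed rate near 5% per year, the planned gap adds less than half a case per site.

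The net direction is not fixed, because an untested tail works the other way and can be larger. The mismatch is small and confined to descriptive secondary endpoints. It is still worth removing, because larger enrollment would not reduce it and the correction is cheap.

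**What to change.** Add to Section 6.4.2: for chlamydia, gonorrhea and syphilis, each woman's time at risk runs from her last negative specimen on or before Enrollment, or from completion of treatment if she was treated before Enrollment, to the last specimen tested for that infection. A woman who was retested at Enrollment and was negative then starts at Enrollment. For the infections tested at the Enrollment Visit, time at risk starts at Enrollment and likewise ends at the last test.

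**Cost.** No new procedures are needed, and the rule uses specimen dates that the study already records. There is slightly more analysis work, because time at risk has to be built separately for each infection. The reported rates change slightly, in either direction. A small amount of pre-enrollment time is counted, with the minor conditioning noted under the objection.

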Each quarter, participants additionally will undergo a structured interview to ascertain HIV risk behaviors and receive HIV/STD pre-test, risk reduction, and post-test counseling. Participants also will undergo pelvic exams with wet mount testing for BV, candidiasis, and trichomoniasis; colposcopic evaluations will be performed at selected sites in accordance with the CONRAD/WHO Manual for the Standardization of Colposcopy for the Evaluation of Vaginal Products, Update 2000. For participants found to have a genital ulcer on pelvic exam, the ulcer will be swabbed for multiplex polymerase chain reaction (PCR) testing at the HPTN Central Lab for chancroid, herpes simplex virus 2 (HSV-2), and syphilis. Follow-up testing for chlamydia, gonorrhea, syphilis, and HIV (see Appendix II) will be performed quarterly, and additionally if clinically indicated. A sample of HIV test results will be confirmed for quality assurance purposes by the HPTN Central Laboratory.

Monthly visits other than those in which pelvic exams are scheduled may take place either on-site, in a participant's home, or at other community-based locations, depending on site capacities and site and participant preferences. If genital symptoms are reported during an off-site visit, the participant will be instructed to report to the on-site clinic as soon as possible for a pelvic exam. Other participant-initiated interim visits may occur at any time during follow-up, for example to obtain additional HIV counseling and testing.

All HIV and STD testing will be performed in the context of pre-test, risk reduction and post-test counseling. Study sites will provide this counseling in accordance with locally-accepted standards of practice and will document their counseling policies and procedures prior to study implementation for purposes of staff training, quality assurance, and study monitoring. In accordance with NIH policies, study participants must receive their HIV test results in order to remain eligible for study participation.

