4.4.2 Clinical Procedures

- Interval (i.e., since last visit) medical and menstrual history and concomitant medication review:
 - -At all visits.
- Pelvic exam with:
 - colposcopy (at selected sites);
 - specimen collection for Gram stain;
 - wet mount for BV, candidiasis, and trichomoniasis; and
 - swab for multiplex PCR if genital ulcer is observed:
 - -Quarterly.
 - -Additionally when clinically indicated.

- Urine collection:
 - -At all visits.
- Blood collection:
 - -Quarterly.
 - -Additionally when clinically indicated.
- Test results disclosure:
 - -As needed at all visits and contacts.
- Treatment for STDs and other infections (except asymptomatic candidiasis); offer of STD testing and treatment for partner(s):
 -When clinically indicated.

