6.2.1 Secondary Endpoints

Consistent with the secondary study objectives, the following will be assessed as secondary endpoints:

- Potential participants screened for the study, and the screening outcome for each screenee.
- Participants enrolled in the study.

- Participants retained in the study until the site-specific study end date.
- Demographic characteristics of women screened for and/or enrolled in the study, including:
 - Age
 - Race/ethnicity
 - Educational level
 - Employment status
 - Income level
- HIV risk behaviors reported by women enrolled in the study, including:
 - Number of sex partners
 - Frequency of vaginal intercourse
 - Frequency of unprotected vaginal intercourse
 - Frequency of anal intercourse
 - Frequency of unprotected anal intercourse
- Prevalent (i.e., at screening/enrollment) and incident (i.e., during follow-up) occurrences of the following:
 - Pelvic exam findings involving deep epithelial disruption
 - Genital ulcer disease
 - Other genital signs and symptoms
 - Bacterial vaginosis
 - Candidiasis
 - Chlamydia infection
 - Gonorrhea infection
 - Syphilis infection
 - Trichomoniasis

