6.3 Accrual, Follow-up, and Sample Size

Each participating study site will target accrual of 240 study participants within the six-month accrual period, with the monthly enrollment targets presented in Section 2.2. Each site also will target retention of 95 percent of enrolled participants annually (or 97.5 percent semi-annually).

As will be described in Section 6.4.2, assessment of the study outcomes related to accrual and retention will not require statistical analysis. However the precision of study estimates of HIV and STD incidence depends on the number of participants enrolled and retained in the study, as well as the "true" seroincidence rate. Shown in Tables 1 and 2 below are the widths of exact 95% confidence intervals around site-specific incidence rates, assuming the accrual schedule presented in Section 2.2 and retention of 97.5 percent of participants semi-annually, with either a sixmonth (Table 1) or twelve-month (Table 2) follow-up period, and an expected 117 and 234 woman-years of follow-up, respectively.

Table 1
95% Exact Confidence Intervals for Infection Rates
Observed in a Six-Month Follow-up Period

Observed in a dix-month i dilow-up i eriod								
No. Infections	Observed	95% Exact						
Observed	Infection Rate	Confidence Interval						
1	1.7%	0.2-6.2%						
2	3.4%	0.9-8.8%						
3	5.1%	1.8-11.2%						
4	6.8%	2.9-13.5%						
5	8.5%	4.0-15.7%						
6	10.3%	5.3-17.9%						

Table 2
95% Exact Confidence Intervals for Infection Rates
Observed in a Twelve-Month Follow-up Period

No. Infections Observed	Observed Infection Rate	95% Exact Confidence Interval
2	1.7%	0.4-4.4%
4	3.4%	1.4-6.7%
6	5.1%	2.6-9.0%
8	6.8%	3.9-11.1%
10	8.5%	5.2-13.2%
12	10.3%	6.5-15.3%

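### Incidence of genital findings and infections counts every occurrence in follow-up, so untreated asymptomatic candidiasis present at enrollment is counted again as incident at later quarterly exams

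*Supplement*

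**What the plan says.** Estimating prevalence and incidence of nine conditions, candidiasis among them, is a secondary objective (Section 2.1.2). Section 6.2 (Secondary Endpoints) lists the endpoints as "Prevalent (i.e., at screening/enrollment) and incident (i.e., during follow-up) occurrences of the following". Section 6.4.2 then gives each site's incidence rate "as the total number of endpoints observed divided by the total number of person-years of follow-up" and adds: "Confidence intervals will be calculated based on Poisson distribution assumptions".

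On detection, Section 2.2 states for the quarterly visits: "Participants also will undergo pelvic exams with wet mount testing for BV, candidiasis, and trichomoniasis". The laboratory tests follow the same rhythm: "Follow-up testing for chlamydia, gonorrhea, syphilis, and HIV (see Appendix II) will be performed quarterly, and additionally if clinically indicated".

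On treatment, Section 3.2 says that women diagnosed at enrollment with infections needing treatment under WHO guidelines ("other than asymptomatic candidiasis) will be offered treatment and may be enrolled after completing treatment and all symptoms have resolved"). The follow-up procedures in Section 4.4.2 carry the same exception: "Treatment for STDs and other infections (except asymptomatic candidiasis").

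The protocol does not restrict the count to first events. It does not require a negative result or clearance before a new event, remove time while infected, or allow for several events in one woman. The letter of amendment does not change Section 6.4.2.

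**The concern.** An incidence rate should count new episodes among women who could have one. The stated numerator has no such condition, and one listed condition is knowingly left in place: a woman may enroll with asymptomatic candidiasis, remain untreated, and be examined again at months 3, 6, 9 and 12. Under the rule as written she contributes to baseline prevalence and then to incidence each time the same infection is seen. The rate becomes a mixture of new infection and point prevalence, biased upward as a measure of new infection.

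A second question is whether a Poisson interval suits a count to which one woman can contribute several times. It suits HIV, where each woman has at most one seroconversion.

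At stake is how far a stated secondary objective can be believed for candidiasis, and to a lesser degree for the other recurrent conditions.

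**Working it through.** **1. The plan's own figures.** Section 6.3 expects 117 and 234 woman-years (WY) per site: 240 × 0.5 × 0.975 = 117 and 240 × 1 × 0.975 = 234. Exact Poisson limits are χ²(0.025; 2x)/(2T) and χ²(0.975; 2x+2)/(2T). With the amended counts, 12 events in 117 WY give 10.3% (5.3–17.9), as printed. For 24 in 234 WY the result is 10.3% (6.6–15.3), against a printed 6.5–15.3. All rates and upper limits match, and lower limits agree within 0.1 point. The tables therefore assume pure Poisson variance.

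**2. What can carry over untreated.**

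| Condition | At enrollment | In follow-up |
|---|---|---|
| Asymptomatic candidiasis | May be present, exempt from treatment | Exempt from treatment |
| Other infections requiring treatment | Treatment completed and symptoms resolved first | Treated |
| Deep epithelial disruption | Must have resolved | No carry-over from enrollment |

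**3. Size of the carry-over.** Inputs from Section 2.2: monthly enrollment of 20, 30, 40, 50, 50, 50, and follow-up to six months after accrual ends. Assumptions: mid-month entry and no loss.

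- Follow-up in months is 11.5, 10.5, 9.5, 8.5, 7.5, 6.5. Woman-years = (230 + 315 + 380 + 425 + 375 + 325)/12 = 170.8.
- The first 90 women have three quarterly exams and the other 150 have two.
- Let p be the prevalence at enrollment and s the chance that a positive exam is followed by a positive one. Carried-over positives = 90p(s + s² + s³) + 150p(s + s²).

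| p | s | Events | Per 100 WY |
|---|---|---|---|
| 0.05 | 0.30 | 1.9 + 2.9 = 4.8 | 2.8 |
| 0.10 | 0.50 | 7.9 + 11.3 = 19.1 | 11.2 |
| 0.15 | 0.70 | 20.7 + 26.8 = 47.5 | 27.8 |

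On the plan's own woman-years, with p = 0.10 and s = 0.50:
- Two exams: 240 × 0.10 × 0.75 = 18 events, and 18/117 = 15.4 per 100 WY.
- Four exams: 240 × 0.10 × 0.9375 = 22.5 events, and 22.5/234 = 9.6 per 100 WY.

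This counts only infections present at enrollment. Untreated infections acquired in follow-up and seen again add more. In a simulation with four exams, 20 new infections per 100 WY and s = 0.50, counting every positive gives 1.54 times the new-episode count if no woman is positive at enrollment, and 2.06 times if 10% are.

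**4. The denominator.** Infected time left in the denominator works the other way, but weakly. Allow one infected quarter after each positive, in the central case. The 9 positive women with three exams give 9 × 1.875 × 0.25 = 4.2 WY, and the 15 with two exams give 15 × 1.75 × 0.25 = 6.6 WY. The total is 10.8 of 170.8 WY, about 6%. A rate of 20 per 100 WY at risk would fall to about 18.7, a loss of 1.3 against a gain of 11.2.

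**5. The intervals.** Simulated coverage of the exact 95% Poisson interval for 240 women, with gamma-distributed risk between women (variance 1 / 2, assumed). In the capped rows a woman can have at most one positive per quarterly exam, calibrated to the same observed rate.

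| Model | Rate per 100 WY | Variance ratio | Coverage, % |
|---|---|---|---|
| Unlimited events, 171 WY | 60 | 1.4 / 1.9 | 91 / 86 |
| Unlimited events, 171 WY | 100 | 1.8 / 2.5 | 86 / 80 |
| Capped, 2–3 exams, 171 WY | 60 | 1.0 / 1.1 | 96 / 94 |
| Capped, 2–3 exams, 171 WY | 100 | 0.9 / 1.1 | 96 / 94 |
| Capped, 4 exams, 234 WY | 60 | 1.2 / 1.4 | 93 / 90 |
| Capped, 4 exams, 234 WY | 100 | 1.2 / 1.5 | 92 / 89 |

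Across runs with slightly different follow-up, the four-exam range is about 90–94%, with 89% the lowest. At 10 per 100 WY coverage is nominal or slightly above in the capped runs. With equal risk and no persistence, the variance ratio under quarterly testing is below 1.

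Persistence also clusters events. With 20 new infections per 100 WY, 10% positive at enrollment and s = 0.50, the variance ratio for all positives is about 1.3 with two exams and 1.75 with four. Counting new episodes only brings it to about 0.9.

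**The case against.** The best defence is that the protocol nowhere says that each positive wet mount is a new event. The contrast between prevalent and incident could be taken to exclude a continuing infection, and episode rules often sit in an analysis plan, which is not shown. This has some weight, but the protocol is not silent here: it states a numerator, a denominator and an interval method. A programmer following them would count the repeat positives.

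It is also fair that total episodes per person-year is a legitimate measure of burden, that these rates are secondary and descriptive with no test or threshold attached, and that every figure for the size of the bias rests on assumed inputs. All of that stands and limits the weight of the point.

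A reader might infer two stronger claims.

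- **That all listed infections persist and are recounted.** The documents do not support this. Asymptomatic candidiasis is the only infection expressly exempt from treatment.
- **That repeat events in one woman make the Poisson intervals badly too narrow, with coverage of 80–91%.** Those figures come from a model with unlimited events per woman, which does not fit detection at quarterly exams. Repeats alone do not narrow the intervals; unequal risk or persistence is needed. One caveat: the capped runs in step 5 leave out persistence and the extra clinically indicated exams, either of which could add clustering.

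**Conclusion.** The point holds for the counting rule. As written, the candidiasis incidence rate counts persisting untreated infections as new. Under 10% prevalence and 50% quarter-to-quarter persistence this adds about 19 events per site, or 11 per 100 WY (3 to 28 over 5–15% and 30–70%). Both inputs are assumptions. For the other infections, the same gap matters only for treatment failure or findings not yet resolved at the next exam.

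The interval question is conditional and smaller. At 60–100 events per 100 WY and between-woman variance 1–2, coverage is about 94–96% with two to three exams and about 90–94% with four. It is not a concern for rare endpoints.

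The primary HIV seroincidence analysis is unaffected. The change is worth making because it concerns a stated objective and costs little.

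**What to change.** In Sections 6.2 and 6.4.2:

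1. Count an occurrence as incident only if the preceding exam or test for that condition was negative, or resolution was documented in between.
2. Count person-time only while the woman is at risk of a new episode. A simpler alternative is first-event incidence among women negative at enrollment, with time ending at the first event.
3. If several episodes per woman are counted, base intervals on a woman-level robust variance. Keep the Poisson interval for HIV and for first-event rates.
4. If total positives are also wanted as a measure of burden, report them separately under that name.

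No new data and no change to treatment or visits are needed, since the quarterly results are already collected. The cost is wording and a few lines of code. The downside is lower reported rates where conditions persist, and some wider intervals.
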